9.1 Definitions

9.1.1 Unanticipated Problems Involving Risk to Subjects or others

Any incident, experience, or outcome that meets all of the following criteria:

- Unexpected in nature, severity, or frequency (i.e. not described in study-related documents such as the IRB-approved protocol or consent form, the investigators brochure, etc)
- Related or possibly related to participation in the research (i.e. possibly related means there is a reasonable possibility that the incident experience, or outcome may have been caused by the procedures involved in the research)
- Suggests that the research places subjects or others at greater risk of harm (including physical, psychological, economic, or social harm).

9.1.2 Adverse Event

An **adverse event** (AE) is any unfavorable symptom, sign, illness or experience that occurs at any dose and develops or worsens in severity during the course of the study. Intercurrent illnesses or injuries should be regarded as adverse events. Abnormal results of diagnostic procedures are considered to be adverse events if the abnormality:

CONFIDENTIAL

- results in study withdrawal
- is associated with a serious adverse event
- is associated with clinical signs or symptoms
- leads to additional treatment or to further diagnostic tests

is considered by the investigator to be of clinical significance

9.1.3 Adverse Events of Special Interest

AESIs (serious or non-serious) are defined as AEs of scientific and medical concern specific to the Clovis product or program, for which ongoing monitoring and rapid communication by the Principal Investigator to Clovis can be appropriate. Such an event might warrant further investigation in order to characterize and understand it. Depending on the nature of the event, rapid communication by the Principal Investigator to other parties (eg, regulators) might also be warranted.

Details on Clovis's currently agreed list of AESIs for rucaparib can be found in the current rucaparib IB. The following AESIs are to be reported to Clovis expeditiously within 24 hours of knowledge of the event, during the study through 30 days after receiving the last dose of study treatment, according to the procedures below:

- Myelodysplastic Syndrome and Acute Myeloid Leukemia
- Pneumonitis- including the following irrespective of causality assessment and severity:
 - interstitial lung disease
 - pulmonary fibrosis
 - acute interstitial pneumonitis
 - alveolitis necrotizing
 - alveolitis
 - hypersensitivity pneumonitis
 - organizing pneumonia

9.1.4 Serious Adverse Event

Adverse events are classified as serious or non-serious. A **serious adverse event** is any AE, that is:

- fatal
- life-threatening
- requires or prolongs hospital stay
- results in persistent or significant disability or incapacity
- a congenital anomaly or birth defect
- an important medical event

Important medical events are those that may not be immediately life threatening, but are clearly of major clinical significance. They may jeopardize the subject, and may require intervention to prevent one of the other serious outcomes noted above. For example, drug overdose or abuse, a seizure that did not result in in-patient hospitalization, or intensive treatment of bronchospasm in an emergency department would typically be considered serious.

All adverse events that do not meet any of the criteria for serious should be regarded as **non-serious adverse events**.

Events or Outcomes Not Qualifying as Serious Adverse Events

The following are not considered SAEs and therefore do not need to be reported as such:

- Pre-planned or elective hospitalization including social and/ or convenience situations (eg, respite care)
- Hospital visits of less than 24 hours duration (eg, patient presents to the emergency room, but is not admitted to a ward)
- Overdose of either Clovis study drug or concomitant medication unless the event meets SAE criteria (eg, hospitalization). However, the event should still be captured as a nonserious AE

CONFIDENTIAL

- Events of progression of the patient's underlying cancer as well as events clearly related to progression of the patient's cancer (signs and symptoms of progression) should not be reported as a serious adverse event unless the outcome is fatal within the safety reporting period. If the event has a fatal outcome within the safety reporting period, then the event of Progression of Disease must be recorded as an AE and as a SAE with CTC Grade 5 (fatal outcome) indicated.

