9.11 Investigator Reporting: Notifying Drug Manufacturer

All SAEs, AESIs, and pregnancies, regardless of relationship to study drug, must be reported to the Clovis Oncology within 24 hours of knowledge of the event, during the study through 30 days after receiving the last dose of study treatment, according to the procedures below. After the 30 day specified window, only SAEs considered to be treatment related and all AESIs, regardless of treatment relationship, should be reported. It is important that the investigator provide an assessment of relationship of the SAE or AESI to study treatment at the time of the initial report.

The Clovis or the Investigator's study-specific Serious Adverse Event (SAE)/Adverse Events of Special Interest (AESI) Report Form may be used for reporting SAEs and AESIs. The contact information for reporting of SAEs and AESIs can be found on the SAE/AESI Reporting Form and Pregnancy Report Forms.

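### Section 9.1.4 contradicts itself on whether a serious event treated in the emergency room without admission is an SAE

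*Combined protocol and SAP*

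**What the plan says.** Section 9.1.4 makes an adverse event serious if it meets any one of six criteria. Hospital stay is only one of them; others include life-threatening events and important medical events. The last category is explained as follows: "Important medical events are those that may not be immediately life threatening, but are clearly of major clinical significance". Two of its examples do not depend on admission: "a seizure that did not result in in-patient hospitalization, or intensive treatment of bronchospasm in an emergency department would typically be considered serious".

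The same section then gives a list under the lead-in "The following are not considered SAEs and therefore do not need to be reported as such". It has four items:

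- planned or elective hospitalization, with no exception;
- "Hospital visits of less than 24 hours duration (eg, patient presents to the emergency room, but is not admitted to a ward", with no exception;
- "Overdose of either Clovis study drug or concomitant medication unless the event meets SAE criteria (eg, hospitalization", which is an exception for events that meet SAE criteria;
- progression of the underlying cancer, which "should not be reported as a serious adverse event unless the outcome is fatal within the safety reporting period".

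Under section 9.11, SAEs, AESIs and pregnancies, whatever their relationship to the drug, "must be reported to the Clovis Oncology within 24 hours of knowledge of the event".

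**The concern.** An event such as bronchospasm treated intensively in an emergency department and then sent home fits two statements in one section. It is typically serious as an important medical event, and it is a short hospital visit that is not an SAE. A site cannot follow both, and the section does not say which prevails.

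The label matters because some reporting duties depend on it. If the exclusion prevails, the manufacturer does not receive the event within 24 hours and the independent medical monitor, who can stop enrollment, does not see it as an SAE. The exclusion works by place and length of care, whereas the criteria it would override concern the gravity of the event.

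**Working it through.** The plan states no figure on this point and no arithmetic applies. The check is a comparison of passages.

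1. **The definition and the exclusion.** The criteria in 9.1.4 are alternatives, so an event can be serious without any hospital stay. The lead-in to the exclusion list removes SAE status as a whole; it does not switch off one criterion. The short-visit item gives as its example an emergency room visit without admission, which is the setting that the bronchospasm example can describe. The conflict therefore arises on the section's own example.

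2. **The exceptions in the list.** The overdose and progression items each contain an exception. The short-visit item contains none, so a reader may conclude that none applies. The elective-hospitalization item has none either, but it concerns planned stays and does not collide with any example of a serious event.

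3. **Whether another section restores SAE status.** Section 9.8 requires SAE reporting of AEs that lead to or prolong hospitalization. It does not reach a visit without admission, and it gives way to contrary instructions elsewhere in the protocol. No other section restores the status.

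4. **What depends on SAE status.**
   - Section 9.11: the 24-hour report to the manufacturer regardless of causality, through 30 days after the last dose.
   - Section 9.10: the instruction to report a serious AE to the manufacturer and the IRB.
   - Section 9.14: the medical monitor's review of all SAEs.

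5. **What does not depend on it.**
   - AESIs go to the manufacturer within 24 hours whether serious or not (9.1.3, 9.11). The events listed in the protocol are MDS/AML and pneumonitis, so the seizure and bronchospasm examples are not covered.
   - Grade 3 or higher events go to the DSMC within 10 days (9.12). Grade 3 or 4 events are exempt if judged clearly unrelated to protocol therapy, or probably or definitely related to progression or to an FDA-approved agent.
   - Unexpected deaths go to the DSMC within one business day and other deaths within 30 days. Deaths more than 30 days after the last study treatment in subjects who are off study are generally not reportable (9.12).
   - Unexpected events related to the research go to the IRB within 10 working days, serious or not (9.12).
   - All AEs are followed (9.5, 9.9). Only the added requirement to determine the final outcome of SAEs still ongoing at the end of the study period is tied to the label.

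6. **Effect on the analysis.** The safety endpoint is the incidence of AEs, laboratory abnormalities and dose modifications (3.2.2, 8.2), and toxicities are graded and tabulated (8.4). An event enters those tables whatever its SAE label.

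**The case against.** The strongest reply is that the item describes a care setting and not an adverse event. Read with the elective-hospitalization item above it, it only says that a short visit does not count as a hospital stay. The overdose and progression items name events and so need exceptions; the first two name encounters and arguably do not. The bronchospasm example stands in the same section and would guide a sensible site. This is a plausible reading and probably the intended one. It is not written, however, and the lead-in says that the listed items are not SAEs at all.

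A reader might go further and make four inferences that the documents do not support:

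- **That these events go unreported.** The routes in step 5 of the check remain. The IRB loss is especially narrow, because 9.10 refers to 9.12, where unexpected related events are reportable whether serious or not.
- **That deaths in the emergency room disappear.** A fatal event is serious by definition, and the DSMC has its own rules for deaths. Treating such a death as a non-SAE is a strained use of the item.
- **That a 24-hour report becomes a 10-day report.** These go to different recipients. The DSMC's time limit does not change; what may be lost is the report to the manufacturer.
- **That SAE incidence would be understated by a known amount.** One patient in 42 is 1/42 = 2.4 percentage points, but the documents give no rate for such events and SAE incidence is not a stated endpoint. Any assumed number of missed patients would be a guess.

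**Conclusion.** Section 9.1.4 contradicts itself, and the passages should be reconciled. The contradiction is shown by the section's own emergency-department example and needs no outside assumption. Its consequences depend on a site applying the short-visit item literally. In that case an otherwise serious event managed without admission would lose the 24-hour manufacturer report, the serious-event report under 9.10 and the medical monitor's SAE review. Most of the weight lies on the first and third of these.

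The number of patients affected cannot be estimated from the documents. The AE and toxicity tables, the PFS6 analysis and its power do not change. This is a wording fault in safety reporting that should be corrected; it is not a flaw in the trial's design.

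**What to change.** Limit the item to the hospitalization criterion. Suggested wording: *Hospital visits of less than 24 hours without admission do not by themselves meet the hospitalization criterion; the event is still an SAE if it meets any other criterion in 9.1.4.* This follows the form of the overdose item.

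In the same edit, reconcile the two overdose statements: 9.1.4 names drug overdose among events that are typically serious, and then makes overdose non-serious by default in the exclusion list.

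The cost is a short amendment and possibly a few more SAE reports. No treatment, visit or analysis changes.

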9.2 Adverse Event Reporting Period

The study period during which adverse events must be reported is normally defined as the period from the initiation of any study procedures to the end of the study treatment follow-up. For this study, the study treatment follow-up is defined as 30 days following the last administration of study treatment.

9.3 Preexisting Condition

A preexisting condition is one that is present at the start of the study. A preexisting condition should be recorded as an AE if the frequency, intensity, or the character of the condition worsens during the study period.

9.4 General Physical Examination Finding

At screening, any clinically significant abnormality should be recorded as a preexisting condition. At the end of the study, any new clinically significant findings/abnormalities that meet the definition of an AE must also be recorded and documented as an AE.

9.5 Post-Study Adverse Event

All unresolved AEs should be followed by the investigator until the events are resolved, the subject is lost to follow-up, or the AE is otherwise explained. At the last scheduled visit, the investigator should instruct each subject to report any subsequent event(s) that the subject, or the subject's personal physician, believes might reasonably be related to participation in this study. The investigator should notify the Principal Investigator of any death or AE occurring at any time after a subject has discontinued or terminated study participation that may reasonably be related to this study. The Principal Investigator should also be notified if the investigator should become aware of the development of cancer or of a congenital anomaly in a subsequently conceived offspring of a subject that has participated in this study.

9.6 Abnormal Laboratory Values

An abnormal laboratory value that is not already associated with an AE is to be recorded as an AE only if any one of the following criteria is met:

- an action on the study drug is made as a result of the abnormality
- intervention for management of the abnormality is required
- at the discretion of the investigator should the abnormality be deemed clinically significant

9.7 Pregnancy or Drug Exposure

If a patient becomes pregnant during the study the investigator is to stop dosing with study drug(s) immediately.

A pregnancy is not considered to be an AE or SAE; however, any pregnancy occurring in a study patient or partner of a study patient during study participation or within 6 months of last dosing for female patients and 3 months for partners of male patients must be reported to Clovis using the Pregnancy Report Form within the

CONFIDENTIAL

This material is the property of the University of Pennsylvania.

same timelines as an SAE. A pregnancy should be followed through to outcome, whenever possible. Once the outcome of the pregnancy is known, the Pregnancy Outcome Report Form should be completed and reported to Clovis. AEs, SAEs, or AESIs that occur during pregnancy will be assessed and processed according to the AE or SAE/AESI processes using the appropriate AE or SAE/AESI forms

9.8 Hospitalization, Prolonged Hospitalization or Surgery

Any AE that results in hospitalization or prolonged hospitalization should be documented and reported as an SAE unless specifically instructed otherwise in this protocol. Any condition responsible for surgery should be documented as an AE if the condition meets the criteria for an AE.

Neither the condition, hospitalization, prolonged hospitalization, nor surgery are reported as an AE in the following circumstances:

- Hospitalization or prolonged hospitalization for diagnostic or elective surgical procedures for a preexisting condition. Surgery should **not** be reported as an outcome of an AE if the purpose of the surgery was elective or diagnostic and the outcome was uneventful.
- Hospitalization or prolonged hospitalization required to allow efficacy measurement for the study.
- Hospitalization or prolonged hospitalization for therapy of the target disease of the study, unless it is a worsening or increase in frequency of hospital admissions as judged by the clinical investigator.

9.9 Recording of Adverse Events

At each contact with the subject, the investigator must seek information on adverse events by specific questioning and, as appropriate, by examination. Information on all adverse events should be recorded immediately in the source document, and also in the appropriate adverse event module of the case report form (CRF). All clearly related signs, symptoms, and abnormal diagnostic procedures results should be recorded in the source document, though should be grouped under one diagnosis. All adverse events occurring during the study period must be recorded. The clinical course of each event should be followed until resolution, stabilization, or until it has been determined that the study treatment or participation is not the cause. Serious adverse events that are still ongoing at the end of the study period must be followed up to determine the final outcome. Any serious adverse event that occurs after the study period and is considered to be possibly related to the study treatment or study participation should be recorded and reported immediately.

9.10 Reporting of Adverse Events

Investigators must conform to the AE reporting timelines, formats and requirements of the various entities to which they are responsible, but at a minimum those events that must be reported are those that are:

- Related to study participation,
- Unexpected, and
- Serious or involve risks to subjects or others

If the AE is considered serious, Principal Investigator should report this event to Clovis and to their IRB (reference Section 9.12). An event may qualify for expedited reporting to regulatory authorities if it is a suspected unexpected serious adverse reaction (SUSAR) in line with relevant regulations (reference Section 9.13)

If the report is supplied as a narrative, the minimum necessary information to be provided at the time of the initial report includes:

- Study identifier
- Study center
- Subject number
- Investigational study product
- A description of the event

CONFIDENTIAL

This material is the property of the University of Pennsylvania.

- Date of onset
- Current status
- Whether study treatment was discontinued
- The reason why the event is classified as serious
- Investigator assessment of the association between the event and study treatment.

9.11 Investigator Reporting: Notifying Drug Manufacturer

All SAEs, AESIs, and pregnancies, regardless of relationship to study drug, must be reported to the Clovis Oncology within 24 hours of knowledge of the event, during the study through 30 days after receiving the last dose of study treatment, according to the procedures below. After the 30 day specified window, only SAEs considered to be treatment related and all AESIs, regardless of treatment relationship, should be reported. It is important that the investigator provide an assessment of relationship of the SAE or AESI to study treatment at the time of the initial report.

The Clovis or the Investigator's study-specific Serious Adverse Event (SAE)/Adverse Events of Special Interest (AESI) Report Form may be used for reporting SAEs and AESIs. The contact information for reporting of SAEs and AESIs can be found on the SAE/AESI Reporting Form and Pregnancy Report Forms.

9.12 Investigator Reporting: Notifying the Penn IRB

This section describes the requirements for safety reporting by investigators who are Penn faculty, affiliated with a Penn research site, or otherwise responsible for safety reporting to the Penn IRB. The University of Pennsylvania IRB (Penn IRB) requires expedited reporting of those events related to study participation that are unforeseen and indicate that participants or others are at increased risk of harm. The Penn IRB will not acknowledge safety reports or bulk adverse event submissions that do not meet the criteria outlined below. The Penn IRB requires researchers to submit reports of the following problems within 10 working days from the time the investigator becomes aware of the event:

- Any adverse event (regardless of whether the event is serious or non-serious, on-site or off-site) that occurs any time during or after the research study, which in the opinion of the principal investigator is:

Unexpected (An event is “unexpected” when its specificity and severity are not accurately reflected in the protocol-related documents, such as the IRB-approved research protocol, any applicable investigator brochure, and the current IRB-approved informed consent document and other relevant sources of information, such as product labeling and package inserts.)

AND

Related to the research procedures (An event is “related to the research procedures” if in the opinion of the principal investigator or sponsor, the event was more likely than not to be caused by the research procedures.)

Reporting Process

Unanticipated problems posing risks to subjects or others as noted above will be reported to the Penn IRB using the form: “Unanticipated Problems Posing Risks to Subjects or Others Including Reportable Adverse Events” or as a written report of the event (including a description of the event with information regarding its fulfillment of the above criteria, follow-up/resolution and need for revision to consent form and/or other study documentation).

Copies of each report and documentation of IRB notification and receipt will be kept in the Clinical Investigator's study file.

Other Reportable Events:

CONFIDENTIAL

For clinical drug trials, the following events are also reportable to the Penn IRB:

- Any adverse experience that, even without detailed analysis, represents a serious unexpected adverse event that is rare in the absence of drug exposure (such as agranulocytosis, hepatic necrosis, Stevens-Johnson syndrome).
- Any adverse event that would cause the sponsor to modify the investigators brochure, protocol or informed consent form, or would prompt other action by the IRB to assure protection of human subjects.
- Information that indicates a change to the risks or potential benefits of the research, in terms of severity or frequency. For example:
 - An interim analysis indicates that participants have a lower rate of response to treatment than initially expected.
 - Safety monitoring indicates that a particular side effect is more severe, or more frequent than initially expected.
 - A paper is published from another study that shows that an arm of your research study is of no therapeutic value.
- Change in FDA safety labeling or withdrawal from marketing of a drug, device, or biologic used in a research protocol.
- Breach of confidentiality
- Change to the protocol taken without prior IRB review to eliminate apparent immediate hazard to a research participant.
- Incarceration of a participant when the research was not previously approved under Subpart C and the investigator believes it is in the best interest of the subject to remain on the study.
- Complaint of a participant when the complaint indicates unexpected risks or the complaint cannot be resolved by the research team.
- Protocol violation (meaning an accidental or unintentional deviation from the IRB approved protocol) that in the opinion of the investigator placed one or more participants at increased risk, or affects the rights or welfare of subjects.

Abramson Cancer Center Data Safety Monitoring Committee (DSMC):

Every effort should be made to report an event as a diagnosis, not as a list of symptoms. Symptoms that led to the diagnosis should be included in the event description, but should not be the actual event.

1. Unless covered by exclusions below, Grade 3 or higher events must be reported within 10 days of knowledge.
2. All unexpected deaths within one business day of knowledge.
3. All others deaths within 30 days of knowledge. Deaths of subjects off-study for greater than 30 days from the last study treatment/intervention are not reportable unless a longer time frame is specified in the protocol.

EXCEPTIONS to AE/SAE Reporting:

- A) Grade 3 or 4 events that are judged by a study investigator to be clearly unrelated to protocol therapy.
The reason for determining that the event is unrelated must be clearly documented in the EMR.
- B) Grade 3 or 4 events that are probably or definitely related to progression of disease as judged by a study investigator. The fact that this event is related to disease progression must be clearly document in the EMR.
- C) Grade 3 or 4 events that are probably or definitely related to an FDA approved agent. The fact that this event is related to the FDA approved agent must be clearly documented in the EMR..

SAEs will be submitted to the DSMC through the Velos Clinical Trial Management System.

Reportable Events:

CONFIDENTIAL

Exception

A one time, intentional action (planned prospectively) or process that departs from the IRB and CTSRMC approved study protocol, intended for one occurrence. Advance documented IRB and DSMC approval is required.

For in-house studies with a Medical Director or Safety Monitoring Committee (not DSMB), approval must be obtained from the Medical Director or Safety Monitoring Committee prior to submitting your exception request to the DSMC.

The following information must be contained in your exception request:

- When it is needed and why it is needed in that timeframe
- Has the Medical Monitor or Sponsor approved and provide the documentation of approval
- Is this an exception from eligibility, treatment, disease progression, study calendar windows, etc.
- Why the exception is needed (cite the section(s) of the protocol) along with the full clinical details of the subject. This must be determined by the sub-Investigator or PI.
- The reason why the protocol currently doesn't allow the situation for which an exception is being requested. This must be determined by the sub-Investigator or PI.
- If there are plans to amend the protocol and if not, why not.
- If additional follow-up or interventions will be required in order to protect the subject as a result of this exception.

Study Exceptions the DSMC may Reject:

Exceptions to eligibility, treatment/dosing, contraindicated treatment/therapies/interventions or safety tests for the following types of studies may be rejected by the DSMC:

1. Any investigator-initiated treatment study.
2. Any treatment study involving on-campus manufacturing of any component, regardless of sponsor.

To seek approval, you must provide the DSMC with strong and compelling scientific and clinical information to support your request. You should also include a statement explaining whether or not the protocol will be amended. If the protocol will not be amended your reasoning must be provided. If this situation is likely to happen again, the DSMC will require a protocol amendment.

Deviation

Any unintentional action or process that departs from IRB approval and is identified retrospectively. The deviation is reportable to the DSMC and the IRB within 10 days from the time the event becomes known to the study team only when: one or more participants were placed at increased risk of harm, or, the event has the potential to occur again, or the event has the potential to qualify as serious or continuing noncompliance.

If the PI determines that a deviation has **any potential** to impact participant safety (harm and/or risk), or the integrity of data produced from the participant, or some other overall impact on the study, the PI must report the deviation to the IRB and DSMC as described above. The IRB will make the final assessment of the impact. The DSMC will assess for additional safety and scientific integrity concerns.

The following information must be contained in your deviation report:

- When it happened? When the study team (any member) became aware
- The full description of the deviation including important dates, test results, actions taken towards the subject, etc. Also, why it happened and how it was identified.
- Was the Medical Monitor or Sponsor notified. If so, their response?
- The PIs assessment of the impact on risk, safety and/or outcome. If no impact, why. If impact, what and what will happen next.

CONFIDENTIAL

- The corrective actions that have been implemented to date and the impact of those corrective action plans.
- Future corrective action plans (if applicable) and the impact of those plans.
- If there are plans to amend the protocol (if applicable to prevent future deviations) and if not, why not.

If the PI determines that the event had **no potential** to impact participant safety (harm and/or risk) or the integrity of data produced from the participant, the PI must fully document his/her rationale for each category (risk, harm, and participant data).

